current use (\leq 4 weeks of study entry) of any PAP-therapy (e.g., CPAP or NPPV); sleep apnea as follows: STOPBang scores \geq 5 or STOPBang score \geq 2 plus BMI $>$ 35 kg/m²; or Berlin questionnaire scores suggesting high likelihood of sleep apnea with increased risk of sleep-related accident (e.g., occupation as a commercial driver or pilot); or excessive daytime sleepiness (i.e., either of High (>15) score on the Epworth Sleepiness Scale or “fall asleep” accident or “near miss” accident in prior 12 months).

c) Local Number of Subjects

Thirty subjects will be accrued locally for this study.

We expect few screen failures.

d) Study-Wide Number of Subjects

If this is a multicenter study, indicate the total number of subjects to be accrued across all sites. – Not applicable.

e) Study Timelines

- Subjects will be followed for 90 days with regular telephone follow-up and clinic visits throughout.
- Subjects will be enrolled over a period of 12 months.
- The investigators will complete the data analysis approximately 18 months after the first subject is enrolled.

f) Study Endpoints

The primary endpoints of this study are the feasibility of oxygen therapy by HNHF-O2 at home over a 90-day period in terms of tolerance and hours of use. Descriptive statistics will be used to characterize the patient population in terms of demographic factors and severity of airflow obstruction. Changes in PaO₂, PaCO₂ and pH across the days will be done by analysis of variance. The effect of baseline PaCO₂ on change in PaCO₂ with HNHF-O2 therapy will be analyzed as an independent effect on change in PaCO₂ levels with HNHF-O2. Changes in respiratory rate, heart rate, blood pressure accessory muscle use will also be assessed by analysis of variance. Patient tolerance and side effects will also be measured across days of use per patient and across days in all patients as group trends. Hours of use per device log and per patient diary will be independently analyzed and compared to one another. The impact on change in exacerbation frequency and severity will be analyzed. Changes in spirometry, 6MWD, GOLD grade and class and BODE scores prior to and after 90 days of HNHF-O2 will be analyzed.

g) Procedures Involved in the Human Research

[figure not shown]
An overview of the study is provided in the figure below.

Outpatient HNHF-O2 Protocol

Version 3.0

10/06/2017

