- Side effects related to high flow nasal administration: nasal dryness, epistaxis, nasal crusting, eye discomfort, pressure discomfort, increase rhinitis, decreased smell, post nasal drip, hoarseness
- Hours of daily use of HNHF-O2 therapy
- Daily record keeping of daily diary review

At day 90 ± 2 the following will be measured:

- Measurements of vital signs (heart rate, respiratory rate and blood pressure)
- Respiratory patient-discomfort and dyspnea assessed using an unmarked 100 mm visual analogic scale from “no discomfort” to “maximal imaginable discomfort”
- Likert scale model indicating marked improvement (+2), slight improvement (+1), no change (0), slight deterioration (-1) and marked deterioration (-2)
- Side effects related to high flow nasal administration: nasal dryness, epistaxis, nasal crusting, eye discomfort, pressure discomfort, increase rhinitis, decreased smell, post nasal drip, hoarseness
- Hours of daily use of HNHF-O2 therapy
- Daily record keeping of daily diary review
- Arterial blood gas on room air after the participant has been off the Airvo Device for 20 minutes.
- Pre-and post-bronchodilator spirometry

Outpatient HNHF-O2 Protocol

Version 3.0

10/06/2017

- CAT, SGRQ
- 6 Minute walk test
- GOLD grade and group will be classified
- BODE scores will be calculated.

Application of HNHF-O2 therapy. During HNHF-O2, oxygen will be passed through a heated humidifier (myAIRVO 2, Fisher and Paykel Healthcare) and applied continuously through large-bore binasal prongs, with a gas flow rate of 20-35 liters per minute (or as high as tolerated). Temperature will be adjusted based on patient's comfort and range from 34-37 degrees based on prior experience. The fraction of oxygen in the gas flowing in the system will be adjusted to maintain an SpO2 of 90% or more. High-flow oxygen will be applied at the highest tolerated flow up to 35 lpm at home. Meter time and patient's log of hours of daily use will be measured and compared.

Hypercapnic COPD patients are encouraged to use supplemental oxygen therapy on a continuous basis. The use of the humidified nasal high-flow device in this protocol is not expected to change the total number of hours that the patient receives supplemental oxygen; however it will change the manner in which the oxygen is delivered. Patients will be encouraged to use the device for oxygen delivery as many hours per day as possible.

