During the subject's hospitalization various medications including bronchodilators, corticosteroids, and antibiotics may be administered to manage the COPD exacerbation. These will be prescribed by the subject's physician as standard of care. The subject's usual maintenance medications will be prescribed as clinically indicated as standard of care. Other testing and procedures (such as laboratory testing and radiographic imaging) may be performed. These would also be standard of care.

myAIRVO 2 device. The myAIRVO 2 device is a humidifier with integrated flow generator that delivers high flow warmed and humidified respiratory gases to spontaneously breathing patients through a variety of patient interfaces. It is intended for the treatment of spontaneously breathing patients who would benefit from receiving high flow warmed and humidified respiratory gases. The myAIRVO 2 is for patients in homes and long-term care facilities. The flow may be from 2 – 60 L/min depending on the patient interface. There are few expected side effects of using the myAIRVO 2 device – if the humidification is too low, the subject may experience nasal/throat discomfort or epistaxis.

Optiflow+ nasal cannula. The Optiflow+ nasal cannula is a nasal cannula patient interface for delivery of humidified respiratory gases. There are few expected side effects of using the Optiflow+ nasal cannula – some minor irritation or sensitivity may occur where the cannula sits on the skin.

Telephone calls. Subjects will receive telephone calls on days 1, 3, 17, 37, 58, 80 (after initiation of HNHF-O2) to determine vital status, assess adverse events, compliance with the device, and to answer any questions they may have regarding the study. In addition to the scheduled telephone calls, the subject may receive phone calls from the monitors of the electronic daily diary if the subject fails to report symptoms for three consecutive days.

h) Data and Specimen Banking

Not applicable.

i) Data Management

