The primary endpoints of this study are the feasibility of oxygen therapy by HNHF-O2 at home over a 90-day period in terms of tolerance and hours of use. Descriptive statistics will be used to characterize the patient population in terms of demographic factors and severity of airflow obstruction. Changes in PaO₂, PaCO₂ and pH across the days will be done by analysis of variance. The effect of baseline PaCO₂ on change in PaCO₂ with HNHF-O2 therapy will be analyzed as an independent effect on change in PaCO₂ levels with HNHF-O2. Changes in respiratory rate, heart rate, blood pressure accessory muscle use will also be assessed by analysis of variance. Patient tolerance and side effects will also be measured across days of use per patient and across days in all patients as group trends. Hours of use per device log and per patient diary will be independently analyzed and compared to one another. The impact on change in exacerbation frequency and severity will be analyzed. Changes in spirometry, 6MWD, GOLD grade and class and BODE scores prior to and after 90 days of HNHF-O2 will be analyzed.

This is a pilot study in which the primary outcome is to determine the feasibility of using high-flow nasal oxygen in patients with COPD who have been recently discharged from the hospital with a COPD exacerbation. As such it is not an efficacy trial and is powered based on the ability to detect safety issues or unforeseen problems. The sample size has been estimated based on the method described by Viechtbauer, et.al.⁷

The safety issue we have identified is the need to withdraw therapy because HNHF-O2 is not tolerated by the subject.

The formula for this calculation is based on the probability of observing at least one of these events:

$$P(x > 0) = 1 - (1 - \pi)^n \text{ where}$$

x = the number of events that occur across the total number of participants
and

π = the probability that the event will occur.

Solving for n yields:

$$n = \frac{\ln(1 - \gamma)}{\ln(1 - \pi)}$$

Where γ = the confidence threshold.

Using a 95% confidence threshold and 15% probability that an event (need to discontinue due to intolerance) occurs the sample size required is:

Outpatient HNHF-O2 Protocol

Version 3.0

10/06/2017

$$n = \frac{\ln(1-0.95)}{\ln(1-0.1)} = 28.4 \text{ subjects.}$$

The number of subjects has been increased to 36 to accommodate screen failures and dropouts and to provide evaluable data on 30 subjects.

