All data will be stored on the REDCap website and on password protected files on password protected computers located on the 7th floor of the Kresge Building. This is an area with access restricted to study personnel.

j) Confidentiality

All data will be stored on the REDCap website. The site is part 11 compliant. All study personnel have been trained in human subjects protections and good clinical practices. Study data will only be accessible to study personnel via password protected websites and computer terminals.

k) Confidentiality

All data will be stored on the REDCap website. The site is part 11 compliant. All study personnel have been trained in human subjects protections and good clinical practices. Study data will only be accessible to study personnel via password protected websites and computer terminals.

l) Provisions to Monitor the Data to Ensure the Safety of subjects

This study utilizes an FDA-approved device for the delivery of warmed humidified gases for a medical indication included in the 510(k) approval letter. As such, and because of the limited enrollment in this trial, there is no need for a data and safety monitoring board. Monitoring of the study will be done by the principal investigator on a routine (monthly) basis in conjunction with the study sponsor and the Director of Research at the Temple Lung Center. All adverse events will be reviewed with particular attention paid to those subjects who discontinued use of the device and those where oxygen therapy needed to be intensified in order to maintain adequate oxygenation.

m) Withdrawal of Subjects

Subjects may discontinue participation in the study at any point and for any reason. This decision will not be held against them in any way. If a subject decides to withdraw, the physician will assess their clinical condition and determine the best course of action for the subject. This may include alternative methods of oxygen administration. Any data that is collected up to the point of subject withdrawal will be retained for analysis.

11) Risks to Subjects

History and physical exam, vital signs. These are all procedures routinely performed as standard of care and are not associated with any adverse effects.

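### The tolerance analysis has no rule for patients who stop: one summary counts only days of use, and the group trend leaves open whether patients who withdraw stay in the denominator

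*Combined protocol and SAP*

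**What the plan says.** Section 10(f) states: "The primary endpoints of this study are the feasibility of oxygen therapy by HNHF-O2 at home over a 90-day period in terms of tolerance", with hours of use as the other half. The time course of tolerance is covered by one sentence: "Patient tolerance and side effects will also be measured across days of use per patient and across days in all patients as group trends". Section 10(i) repeats it. It sets two summaries, one per patient and tied to days of use, the other for the group and described as covering all patients.

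Neither section defines tolerance, names a denominator, says how a day off the device is scored, or says how a patient who has stopped enters later time points. Section 10(m) adds: "Any data that is collected up to the point of subject withdrawal will be retained for analysis". No collection after withdrawal and no missing-data rule is described.

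The sample-size text in 10(i) treats stopping as the key event: "The safety issue we have identified is the need to withdraw therapy because HNHF-O2 is not tolerated by the subject". It is not linked to the tolerance analysis.

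Section 10(g) gives a nine-item checklist, beginning "Side effects related to high flow nasal administration: nasal dryness, epistaxis, nasal crusting, eye discomfort". After the start of therapy it is listed for the clinic visits at about Days 7, 28, 49, 70 and 90. The six calls (Days 1, 3, 17, 37, 58, 80) are "to determine vital status, assess adverse events, compliance with the device", without the checklist. The daily diary covers respiratory symptoms, including sore throat and nasal congestion, but is not the device checklist.

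**The concern.** Whether a day is a day of use depends partly on tolerance. A patient with a nosebleed or pressure discomfort may leave the device off, and that day then leaves the per-patient summary. A patient who gives up contributes no further days of use.

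For the group trend, a patient who withdraws has no later value unless a rule supplies one. The patients most likely to be lost this way are those who tolerate the device worst, so a falling side-effect curve could be attrition that reads as adaptation. The study has one arm, so no control group would expose this. The error would favour feasibility, which is what the study sets out to judge.

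**Working it through.** **1. The plan's own figure.** n = ln(1 − γ)/ln(1 − π). With γ = 0.95 and π = 0.10, as in the displayed formula, n = ln(0.05)/ln(0.90) = 28.43, which reproduces the stated 28.4. The text instead says: "Using a 95% confidence threshold and 15% probability that an event (need to discontinue due to intolerance) occurs". With π = 0.15, n = 18.43, which does not match. That mismatch is a separate matter. Here it gives a planning range for intolerance stops among 30 patients: 0.10 × 30 = 3 to 0.15 × 30 = 4.5.

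**2. Group trend.** Assumed, not in the documents: 30 start; 3 or 5 are intolerant, with a side effect on every day of use; they stop at Days 10, 20, 35, 55 and 75 (the first three of these if there are 3); the others have a constant prevalence of 10% or 20%. No patient's own rate changes. The composite counts a patient who has a side effect or has stopped for intolerance. The last column takes tolerating to mean not having stopped for intolerance.

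Five intolerant, others at 10% (25 × 0.10 = 2.5 expected):

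| Day | On device | Side effects among users | Composite, all 30 | Still tolerating, all 30 |
|---|---|---|---|---|
| 7 | 30 | (2.5 + 5)/30 = 25.0% | 25.0% | 30/30 = 100% |
| 28 | 28 | (2.5 + 3)/28 = 19.6% | 25.0% | 28/30 = 93.3% |
| 49 | 27 | (2.5 + 2)/27 = 16.7% | 25.0% | 27/30 = 90.0% |
| 70 | 26 | (2.5 + 1)/26 = 13.5% | 25.0% | 26/30 = 86.7% |
| 90 | 25 | 2.5/25 = 10.0% | 25.0% | 25/30 = 83.3% |

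Other cases, Day 7 to Day 90 among users:
- 3 intolerant, others at 10%: (2.7 + 3)/30 = 19.0% to 2.7/27 = 10.0%.
- 3 intolerant, others at 20%: (5.4 + 3)/30 = 28.0% to 5.4/27 = 20.0%.
- 5 intolerant, others at 20%: (5 + 5)/30 = 33.3% to 5/25 = 20.0%.

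The apparent fall is 8 to 15 percentage points. The composite is flat in every case.

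**3. Per-patient summary, days off.** Assume one patient has 30 problem days in 90 and leaves the device off on 20 of them. On days of use the rate is 10/(90 − 20) = 14.3%; on all days it is 30/90 = 33.3%.

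**4. Per-patient summary, days after stopping.** The effect depends on weighting, which the plan does not give. With five intolerant and the others at 10%, days of use among stoppers total 10 + 20 + 35 + 55 + 75 = 195. Pooling days of use gives (195 + 25 × 90 × 0.10)/(195 + 25 × 90) = 420/2,445 = 17.2%. Averaging patients equally gives (5 × 100% + 25 × 10%)/30 = 25.0%. In neither case does the summary show that five patients stopped.

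**5. Data source.** The checklist is listed at 5 of the 11 contacts after the start of therapy. A patient who stops before the Day 7 visit may never be asked it, and the days-of-use summary has no daily side-effect record behind it.

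**The case against.** A reader might infer that the plan restricts the group trend to current users. It does not: days of use qualifies only the per-patient summary, and the trend refers to all patients. A reader might also infer that stopping the device ends observation. The documents do not say so. Section 10(e) follows subjects for 90 days, and 10(l) speaks of patients who discontinue the device without equating that with leaving the study. A patient who leaves the device off but attends clinic can still be asked the checklist.

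Other provisions soften the problem. Intolerance withdrawal is the event on which the study is sized and would probably be reported beside any trend. Section 10(l) directs safety review to patients who discontinue. Hours of use, the other half of the primary endpoint, can register days off. Early stoppers are called on Days 1 and 3 about adverse events and compliance, so it would be wrong to say that early intolerance goes unasked. The rates used above are assumptions, and on-use side-effect rates are a legitimate description of a device.

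All of this stands, and it limits the claim. None of it supplies a denominator, a rule for a stop in the tolerance analysis, or a value after withdrawal. Nor does it alter the wording of the per-patient summary.

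**Conclusion.** The point holds in two parts of different strength. For the per-patient summary, the loss of off-device days follows from the plan's own unit. For the group trend, the loss of patients who withdraw is a risk left open by a missing rule.

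In the cases worked, attrition alone lowers apparent prevalence by 8 to 15 points between Day 7 and Day 90. This requires that worse-tolerating patients are the ones who stop and that they then contribute no data. The number stopping is close to the plan's own 10% to 15%; the side-effect rates and stopping days are assumed. The documents do not support reading this as a demonstrated bias of known size. It is still more than missing detail, because it touches a primary endpoint, the error would be in the favourable direction, and a less biased summary costs almost nothing.

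**What to change.** In 10(f) and 10(i):

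- Define tolerance. Make the primary summary the proportion of all patients placed on HNHF-O2 at Visit 2 who still tolerate it at each scheduled time to Day 90, with a stop for intolerance counted as not tolerated from that time on.
- Report side-effect rates among current users as a secondary display, with the number still on the device at each time, kept separate from the tolerance measure.

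In 10(g), ask the nine-item checklist, and the reason for any non-use since last contact, on the six scheduled calls and at the contact where a patient reports stopping.

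Days off the device should not automatically be scored as side-effect days. The listed items record no reason for non-use, and a symptom may resolve once the device is off.

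The cost is analysis wording, a few minutes on calls already planned, and a tolerance figure likely to be somewhat less favourable.

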We treat an average of 16,000 outpatients a year; over 50% of these patients carry a diagnosis of advanced lung disease, including COPD, IPF, pulmonary hypertension, and bronchiectasis. We are a major referral center for lung volume reduction surgery.

All physicians, nurses and ancillary staff members will be instructed in the details of this study.

9) Prior Approvals

Not applicable.

10) Study Design

a) Recruitment Methods

Thirty patients hospitalized for acute exacerbation of COPD \leq the last 12 weeks will be enrolled into the study. Subjects will be recruited from the Temple Lung Center clinical practices in Philadelphia and Oaks, PA.

Potential subjects will be recruited during scheduled office visits to the Temple Lung Center offices in Philadelphia and in Oaks, PA. Many of these patients will be those who have been referred to Temple. We will also contact pulmonology practices in the tri-state area through direct mailings and our monthly research fax blast. The Temple Lung Center also maintains an IRB-approved registry of patients who have agreed to be contacted to discuss participation in clinical research trials.

Describe materials that will be used to recruit subjects. Include copies of these documents with the application. – Not applicable

Subjects will receive compensation in the form of a \$25 gift card for each completed visit during their participation in this study.

b) Inclusion and Exclusion Criteria

Consecutive patients \geq 40 years of age or older who are admitted to the hospital for an acute exacerbation of COPD within the past 12 weeks. Patients will have COPD as the primary diagnosis and have smoked > 10 pack years. Patients should be receiving supplemental oxygen as part of their usual clinical care.

Patients must be willing to give informed consent and be willing to participate in measurement of ABGs, brief history and physical examination and answer questionnaires regarding daily use of HNHF-O2 therapy. Women who are pregnant are excluded from this research. Women of childbearing potential will have a urine pregnancy test to ensure that they are not pregnant.

The main exclusion criteria are upper airway or nasal problems that prohibit the use of high flow oxygen and patients with any of the following will be excluded:

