Feasibility of using daily home HNHF-O2 during Sleep and/or Daytime in Hypercapnic COPD patients following recent (< 12 wks.) hospitalization for AECOPD for 90 days

¹ > 40 yrs. Age and Hospitalized for AECOPD; able to sign IC and willing to do tests

² vital signs, respiratory patient discomfort, Likert scale for clinical improvement, dyspnea (modified Borg Score, mMRC) ABG 5 minutes after inspiring O₂ to maintain SaO₂ >90%, spirometry, 6 MWT, questionnaires (CAT, SGRQ), set baseline diary for respiratory symptoms

³ Inquire about any problems and assess for adherence, troubleshoot

⁴ vital signs, respiratory patient discomfort, Likert scale for clinical improvement, dyspnea, side effects of HNHF-O₂, and review daily electronic diary of respiratory symptoms

⁵ Same as #2

Patients who have had a recent COPD exacerbation (<12 weeks since discharge) accompanied with respiratory failure who meet the above inclusion criteria will be considered for participation in the study.

Once informed consent has been obtained patients will be given the opportunity to participate in the sleep substudy until the enrollment goal of ten subjects has been achieved. A separate protocol and consent form has been submitted for this study. The following procedures will be performed as part of the main study:

Outpatient HNHF-O2 Protocol

Version 3.0

10/06/2017

Test	Visit 1 Screening	Visit 1a Baseline	Visit 2 Clinic Placed on HNHF-O2	Visit 3 Phone Call Day 1	Visit 4 Phone call Day 3 ± 3	Visit 5 Clinic Day 7 ± 5	Visit 6 Phone call Day 17 ± 3	Visit 7 Clinic Day 28 ± 5	Visit 8 Phone call Day 37 ± 3	Visit 9 Clinic Day 49 ± 5	Visit 10 Phone call Day 58 ± 3	Visit 11 Clinic Day 70 ± 5	Visit 12 Phone call Day 80 ± 3	Visit 13 Clinic Day 90 ± 5
Screen	X													
Informed Consent	X													
History & Physical		X				X		X		X		X		X
Pregnancy test for women of childbearing potential		X												
Arterial blood gas◆		X	X											x
Pre- and Post- Bronchodilator Spirometry		X												X
6 minute walk distance		X												X
mMRC Questionnaire		X ²												
Borg Questionnaire		X ²	X			X		X		X		X		X
Assess Accessory Muscle use		X	X			X		X		X		X		X
Assess subject comfort		X	X			X		X		X		X		X

Outpatient HNHF-O2 Protocol

Version 3.0

10/06/2017

Test	Visit 1	Visit 1a	Visit 2	Visit 3	Visit 4	Visit 5	Visit 6	Visit 7	Visit 8	Visit 9	Visit 10	Visit 11	Visit 12	Visit 13

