	Screening	Baseline	Clinic Placed on HNHF- O2	Phone Call Day 1	Phone call Day 3 ± 3	Clinic Day 7 ± 5	Phone call Day 17 ± 3	Clinic Day 28 ± 5	Phone call Day 37 ± 3	Clinic Day 49 ± 5	Phone call Day 58 ± 3	Clinic Day 70 ± 5	Phone call Day 80 ± 3	Clinic Day 90 ± 5
Epworth Sleepiness Scale	X													
Berlin Sleep Questionnaire	X													
STOP-Bang Questionnaire	X													
St. George's Respiratory Questionnaire		X												X
GOLD Category		x												
BODE Index		X												X
Daily Diary	X	X	X			X		X		X		X		X
COPD Activity Test		X												X
Review current medications	X	X	X	X	X	X	X	X	X	X	X	X	X	X
Phone call				X	X		X		X		X		X	
Sleep substudy participants														
Insomnia Severity index		X												
Home sleep study		X ¹				X						X		
Epworth Sleepiness		X ²				X ²						X ²		

Outpatient HNHF-O2 Protocol

Version 3.0

10/06/2017

Scale														
-------	--	--	--	--	--	--	--	--	--	--	--	--	--	--

¹ For those subjects enrolled in the sleep substudy the acquaintance and baseline sleep studies must be completed before beginning HNHF-O2

² Questionnaires are done at baseline visit and repeated at home prior to the baseline, day 7, and day 70 sleep studies.

◆ For ABGs, the test will be done on room air after the participant has been off the Airvo device for 20 minutes. If the participant starts to desaturate, then it can be done on 2L of oxygen.

Outpatient HNHF-O2 Protocol

Version 3.0

10/06/2017

There will be collection of demographic data including age, gender, race, current medications, and comorbid conditions. A patient history of duration of the nature and course of prehospital symptoms, past medical history of smoking, and past use of respiratory medications and nonpharmacological therapy for COPD will be elicited. Historical collection of available clinical data including exacerbation history, reports of chest imaging as well as pulmonary function and/or exercise or cardiac data will be collected.

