At baseline, patients will have measurement of vital signs (heart rate, respiratory rate and blood pressure), dyspnea (modified Borg score, mMRC) arterial blood gas after 5 minutes of inspiring supplemental oxygen to keep $\text{SaO}_2 > 90\%$, and use of accessory muscles of ventilation. Patients will have spirometry performed pre-and post-bronchodilator administration. Patients will have assessment of their current respiratory health by completing CAT, mMRC and SGRQ questionnaires. A detailed history of their exacerbation frequency and severity will be obtained. Patients will perform a 6-minute walk test. Patients GOLD grade and group will be classified and patients BODE scores will be calculated.

Patients will be queried regarding the presence and magnitude of complaints of cough and sputum production by using a daily electronic diary for a 2-week period of run in. After the 2-week run-in period the patient will be scheduled to return to initiate HFNC with oxygen therapy.

Electronic daily diary of respiratory symptoms.

- ❖ Breathlessness (Modified Borg Scale)
- ❖ Sputum Quantity, Color, and Consistency
- ❖ Peak Flow Measurements
- ❖ Presence of Temperature Over 100°F
- ❖ Presence of Any Cough, Wheeze, Sore Throat or Nasal Congestion

Outpatient HNHF-O2 Protocol

Version 3.0

10/06/2017

Patients will be seen in clinic and instructed in the use of HNHF-O2 and its proposed benefits. The necessity of compliance and adherence to the treatment plan will be emphasized.

Following the outpatient clinic visit, patients will be set up at home using an established home vendor for respiratory equipment. Patients will continue to report their daily respiratory symptoms via the electronic diary.

Post placement on optimal dose of HNHF-O2 therapy, subjects will be called the next day to determine if there were any problems.

Patients will report to clinic at baseline and then 7 ± 2 , 28 ± 5 , 49 ± 5 , and 70 ± 5 days for the following assessment:

- Measurements of vital signs (heart rate, respiratory rate and blood pressure)
- Respiratory patient-discomfort and dyspnea assessed using an unmarked 100 mm visual analogic scale from “no discomfort” to “maximal imaginable discomfort”
- Likert scale model indicating marked improvement (+2), slight improvement (+1), no change (0), slight deterioration (-1) and marked deterioration (-2)

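### Minor: as planned, neither the before-after change in exacerbations nor the slope of PaCO₂ change on baseline can be read as a response to HNHF-O2

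*Combined protocol and SAP*

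**What the plan says.** The study has one open-label arm. Its primary endpoints are tolerance and hours of use, and section 10(i) disclaims efficacy. Among the other analyses, 10(f) and 10(i) both list:

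- **Exacerbations:** "The impact on change in exacerbation frequency and severity will be analyzed".
- **PaCO₂:** "The effect of baseline PaCO₂ on change in PaCO₂ with HNHF-O2 therapy will be analyzed as an independent effect" on the change in PaCO₂.

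Entry depends on a recent event. Section 10(b) takes patients "who are admitted to the hospital for an acute exacerbation of COPD within the past 12 weeks", which counts from admission. Section 10(g) counts from discharge: "Patients who have had a recent COPD exacerbation (<12 weeks since discharge".

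The pre-treatment exacerbation data are historical. Section 10(g) promises "Historical collection of available clinical data including exacerbation history" and, at baseline, "A detailed history of their exacerbation frequency and severity will be obtained". No look-back period, event definition or rule on the qualifying admission is given.

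The schedule in 10(g) places arterial gases at Visit 1a (headed as baseline), at Visit 2 ("Visit 2 Clinic Placed on HNHF-O2") and at Visit 13 (Day 90). The plan does not say which gases form the change.

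**The concern.** Both results could look like a response to the device when nothing has happened.

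For exacerbations, patients are chosen because they have just had an event. A history window of 12 weeks or more that ends at entry contains that event by construction, while the 90 days on the device carry no such guarantee. The two periods are therefore not comparable, even in patients whose risk never changes.

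For PaCO₂, if the baseline gas is both the predictor and one half of the change score, its measurement error and day-to-day variation enter both sides of the regression with opposite signs. This usually produces a negative slope, which could be taken to mean that the most hypercapnic patients gain most.

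There is no control arm to show what would have happened without the device. What is at stake is the reading of two secondary results. The primary endpoints and the sample size are untouched, and no decision in the documents rests on either result.

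**Working it through.** The plan gives no figure for either analysis. Its one calculation, ln(0.05)/ln(0.9) = 28.4 subjects in 10(i), concerns intolerance. Every rate, variance, multiplier, correlation and SD ratio below is an assumption, shown over a range.

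**(a) Exacerbations, no treatment effect, qualifying event counted**

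Inputs: 84-day selection window (from the 12-week criterion); λ = 0.5, 1, 2 or 3 qualifying events a year; between-patient gamma variance v = 0, 1 or 2; post-discharge rate multiplier k = 1 or 1.5.

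- m = λ × 84/365, and P₀ = (1 + vm)^(−1/v), or e^(−m) if v = 0.
- Expected events in the window, given at least one: c = m/(1 − P₀).
- True yearly rate in selected patients: T = λ[1 − (1 + vm)^(−1/v − 1)]/(1 − P₀), or λ if v = 0.
- Yearly rate before: c × 365/84 (12-week look-back), or c + T × 281/365 (12 months).
- Apparent fall = 1 − kT/before.

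Example, λ = 2 and v = 1: m = 0.460, P₀ = 0.685, c = 1.460, T = 3.370. The before rate is 6.345 (12 weeks) or 4.054 (12 months). With k = 1 the falls are 1 − 3.370/6.345 = 47% and 1 − 3.370/4.054 = 17%. With k = 1.5 the rate after is 5.055, which gives a 20% fall and a 25% rise.

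Apparent fall in % (negative = rise), each cell for v = 0, 1, 2:

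| λ per year | 12 weeks, k = 1 | 12 weeks, k = 1.5 | 12 months, k = 1 | 12 months, k = 1.5 |
|---|---|---|---|---|
| 0.5 | 89, 80, 73 | 84, 71, 60 | 65, 49, 39 | 48, 23, 8 |
| 1 | 79, 66, 57 | 69, 49, 35 | 47, 31, 23 | 21, −4, −15 |
| 2 | 63, 47, 38 | 45, 20, 6 | 28, 17, 12 | −8, −25, −32 |
| 3 | 50, 35, 27 | 25, 2.5, −9 | 19, 11, 8 | −22, −33.5, −38 |

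At a constant rate every scenario shows a fall. At k = 1.5 the 12-month result is a rise in 8 of 12 scenarios. The multiplier that exactly cancels the artefact (before/T) is 1.37–9.2 for 12 weeks and 1.09–2.89 for 12 months.

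Severity shifts in the same way, because only hospitalised events qualify. Take 2 exacerbations a year in all, 35% hospitalised, v = 1 and a 12-month look-back. Then m = 2 × 0.35 × 84/365 = 0.161, c = 1.161 and T = 3.72 for all events. Hospitalised events before: 1.161 + 0.35 × 3.72 × 281/365 = 2.16. Others: 0.65 × 3.72 = 2.42. The hospitalised share is 2.16/4.58 = 47% before against 35% after, with nothing changed.

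**(b) Slope of PaCO₂ change on baseline**

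With X the Visit 1a gas and Y the Day 90 gas, the slope of (Y − X) on X is cov(X,Y)/var(X) − 1 = ρ × (SD_Y/SD_X) − 1.

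- Equal SDs, ρ = 0.6, 0.7, 0.8, 0.9, 0.95: slope −0.40, −0.30, −0.20, −0.10, −0.05. If a 5% test against zero were used with n = 30, it would reject in about 72, 58, 41, 22 and 13% of studies with no effect.
- Unequal SDs: ρ = 0.8 with ratio 1.25 gives 0.8 × 1.25 − 1 = 0; ρ = 0.9 with ratio 1.25 gives +0.125.

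The identity holds in any data. In a simulated sample with a real baseline-dependent effect, the observed slope and the formula using that sample's own ρ and SD ratio were both −0.2278. It cannot separate effect from no effect without outside values.

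**The case against.** The strongest reply is that this is a feasibility pilot that disclaims efficacy, that both analyses are secondary, and that every size above rests on assumed inputs. All of that stands and sets the grade at minor. It does not remove the missing index-event rule, or a description of the exacerbation result as an impact in a one-arm study.

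On (b), the effect named is that of a baseline covariate, which is ordinary regression wording, and the plan names no test of the slope. The rejection rates therefore apply only if such a test were run.

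Four stronger readings are tempting, and the documents do not support them:

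- **A reader might infer that the exacerbation result is bound to show a false fall.** It is not. The qualifying event may turn out not to be counted, and a raised post-discharge rate can reverse the sign.
- **A reader might infer that the PaCO₂ slope must differ from zero.** It can be zero or positive if Day 90 values are more variable than baseline values.
- **A reader might infer that the two periods are measured differently because the diary does not reach back into the history period.** The diary records respiratory symptoms and is nowhere named as the source of on-study exacerbations. Histories at Visits 5, 7, 9, 11 and 13 and the scheduled calls, which assess adverse events, are other routes.
- **A reader might take ρ × (SD ratio) − 1 from the study's own data as a no-effect benchmark.** It equals the observed slope whatever the truth.

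**Conclusion.** The point holds as a minor one about two non-primary analyses.

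(a) If the qualifying admission is counted, selection alone gives an apparent fall of 27–89% (12-week look-back) or 8–65% (12 months). This assumes a constant rate, no treatment effect, 0.5–3 qualifying events a year and gamma variance 0–2. Post-discharge risk may push the other way by an unknown amount, so neither a fall nor a rise can be read as impact.

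(b) If the Visit 1a gas is both the predictor and part of the change, the slope is generally not zero without treatment effect: −0.40 to −0.05 for ρ of 0.6–0.95 with equal SDs. It should not be read as a response to HNHF-O2.

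The mechanisms follow from the entry criterion and from algebra. The sizes do not come from the documents.

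**What to change.** **(a)** Use one event and severity definition for both periods, and record the dates of prior events. Compute the before rate per person-time from history that ends before both the index admission and the 12-week selection window; whether that window runs from admission (10(b)) or discharge (10(g)) must be reconciled. Deleting only the index event from a 12-week window overcorrects: at 2 a year with v = 0, c = 1.248, which leaves 0.248 × 90/84 = 0.27 events per 90 days against a true 2 × 90/365 = 0.49. Report the on-study rate per person-time, with withdrawn subjects contributing up to withdrawal (10(m)), and with a confidence interval that allows for between-patient variation. Replace the word impact with a descriptive comparison. State that a raised post-discharge rate would bias it towards a rise: the expected change is nil at k = 1 but a 50% rise at k = 1.5.

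**(b)** Report the slope as descriptive, and do not interpret it, or a test of it against zero, as a response to the device. Using the Visit 1a gas as predictor and the Visit 2-to-Day 90 change as outcome reduces the coupling, on two conditions. The Visit 2 gas must be confirmed as drawn before device start. The conflicting gas conditions in 10(g) must also be reconciled: the overview footnote and baseline text have supplemental oxygen; the schedule footnote, Day 90 list and study procedures have room air. Some artefact may remain. With correlations of 0.85 (1a with 2), 0.70 (1a with 13) and 0.70 (2 with 13) and equal SDs, the slope is 0.70 − 0.85 = −0.15, with 18% rejection under no effect against 58% for the same-gas analysis.

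**Cost:** wording and one data item. Dated events may be incomplete, since the history is limited to what is available and, per 10(a), "Many of these patients will be those who have been referred to Temple". The exacerbation estimates will look less favourable. The Visit 2 route makes the slope's standard error about 3–12% larger, from √(2/(1 + ρ)) with ρ from 0.9 to 0.6.
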